### Primary Outcome Measures

**Treatment Dropout/Completion.** We will collect data on treatment completion, to include the number of treatment sessions and assessment visits attended, via chart review from CPRS.

**Treatment Non-Compliance.** We will collect data on treatment compliance, including completion of in-session and between-session assignments, as determined by chart review and self-report.

**Satisfaction with Therapy and Therapist Scale - Revised (STTS-R).** The STTS-R is a 13-item Likert-type self-report scale designed to assess patient satisfaction with therapeutic services and providers (Oei & Green, 2008). This instrument will be administered at the post-treatment and 1-month follow-up time-points.

**Technology and Treatment Satisfaction Questionnaire (TTSQ).** The TTSQ is a 14-item self-report measure developed by the investigators. Items assess satisfaction, acceptance, tolerability, perceived utility and treatment outcome-related expectancies related to incorporating the remote affective physiology procedures into the assessment procedures (see below), as well as opinions about incorporating such measures into routine care. Both patients and

providers will complete slightly different versions of this measure, addressing the same items, but adapted appropriately for wording. This instrument will be administered at the post-treatment time-point.

**Clinician-Administered PTSD Scale for DSM-5 (CAPS-5).** The CAPS-5 is a structured interview for diagnosis of PTSD and is widely considered the gold-standard assessment (Blake et al., 1995; F. W. Weathers et al., 2018). The CAPS-5 will be administered at pre-treatment, post-treatment, and the 1-month follow-up visits, and will be used to evaluate inclusion criteria and as a comparative criterion to assess relations between our objective measurements and severity of trauma-related symptoms and functional impairments.

**PTSD Symptom Checklist for DSM-5 (PCL-5).** The PCL-5 is a 20-item self-report measure of PTSD symptom severity based on the DSM-5 (Wortmann et al., 2016). This measure will be administered at pre-treatment, post-treatment, and the 1-month follow-up, serving as a primary self-report outcome measure. It will also be administered at the beginning of each treatment session, to index trajectories of change over the course of treatment.

**Patient Health Questionnaire (PHQ-9).** The PHQ-9 is a 9-item widely used self-report instrument that assesses core symptoms of major depression (Kroenke, Spitzer, & Williams, 2001). As with the PCL-5, the PHQ-9 will serve as a primary outcome measure administered at pre-treatment, post-treatment, and the 1-month follow-up, and just prior to each treatment session.

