## 1.0 Objectives / Specific Aims

The goal of this project is to establish the safety, feasibility, and acceptability of abbreviating and accelerating telehealth-delivered imaginal exposure therapy for post-traumatic stress disorder (PTSD). Importantly, conventional telehealth-delivered Prolonged Exposure (PE) therapy is non-inferior to the conventional, gold standard in-person PE for PTSD (Acierno et al., 2017). Intensive or massed schedules of in-person exposure- based trauma-focused treatments have likewise recently been shown, in a nascent but promising literature, to produce comparable treatment outcomes to conventional once or twice weekly schedules, but importantly, with lower levels of premature dropout (Sciarrino et al., 2020; Zoellner et al., 2017).

**AIM 1: Establish the safety of VVC-delivered massed imaginal exposure for PTSD.** We hypothesize that VVC-delivered, massed imaginal exposure will be safe as indexed by no significant adverse events.

**AIM 2: Establish the feasibility, tolerability, and acceptability of VVC-delivered massed imaginal exposure for PTSD.** We hypothesize that 1) veterans will consider the treatment acceptable and tolerable and that 2) recruitment and retention will be feasible (> 80% retention).

**EXPLORATORY AIM 1: Establish acceptability among stakeholder providers of VVC-delivered massed imaginal exposure for PTSD.** We hypothesize that 1) telemental healthcare providers will consider the treatment acceptable and tolerable and that 2) will be willing to receive training and/or refer patients to such services.

**EXPLORATORY AIM 2: Establish the preliminary efficacy of VVC-delivered massed imaginal exposure for PTSD.** We hypothesize that 1) veterans will demonstrate moderate reductions in posttraumatic stress and associated symptoms and impairment from intake to the end of treatment that will in turn, 2) be maintained or extended at the 1-month post-treatment follow-up.

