## 8.0 Consent Process

All participants will be referred on the basis of a routine intake assessment in the PCT or another VA behavioral health clinic prior to study entry. As indicated above in the eligibility criteria, those who report clinical symptoms that suggest trauma-focused therapy for PTSD is not in their best interests will be excluded from the study and directed to alternate care as recommended by the PCT and their clinical care team. Participants who appear to meet criteria for entry into the study will be informed of the study and if they express interest, they will review

study consent, and HIPAA Authorization with study personnel (PI, study coordinator, or study evaluator).

The consent process and HIPPA authorization procedures will be completed electronically through VVC or another VA-approved videoconferencing platform, following all VA institutional guidelines pertaining to the consent and authorization procedures. Consent documents will be provided by mail, or through secure messaging, then subsequently reviewed with study personnel at the first study visit (i.e., the pre-treatment or baseline assessment). During review of consent, study staff will detail study procedures and ensure that patients understand what components are part of the study procedures and what is part of standard treatment for PTSD. Study staff will ensure that potential participants understand the study and are interested and able to complete study procedures prior to providing signed informed consent. Participants will receive in the consent document emergency contact information for use in case of acute exacerbation of symptoms. Participants will be informed that they can withdraw from the study at any time and receive alternate care outside of the study. Participants will also be informed that if they report imminent suicidality or intolerance for study procedures at any point during the protocol, they may be withdrawn from the study and receive alternate care as appropriate (i.e., inpatient hospitalization, treatment in outpatient psychiatry, etc.).

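### Aim 2 needs Veterans' view of whether daily telehealth exposure is tolerable, but the only measure described as covering tolerability (the TTSQ) concerns the remote physiology procedures

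*Combined protocol and SAP*

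**What the plan says.** Section 1.0 sets Aim 2 as "Establish the feasibility, tolerability, and acceptability of VVC-delivered massed imaginal exposure for PTSD". Its first hypothesis is that "veterans will consider the treatment acceptable and tolerable". The rater is the Veteran and the object is the treatment.

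Section 9.0, under Primary Outcome Measures, lists two patient-rated satisfaction scales. The STTS-R is "designed to assess patient satisfaction with therapeutic services and providers". The TTSQ has 14 items and was written by the investigators. Its content is given as satisfaction and acceptance, "tolerability, perceived utility and treatment outcome-related expectancies related to incorporating the remote affective physiology procedures" into the assessments, "as well as opinions about incorporating such measures into routine care". Veterans fill in one version, and "providers will complete slightly different versions of this measure, addressing the same items".

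The caption to Figure 1 says that self-reported tolerability of the procedures will be gathered from participants and providers, without saying which procedures. The Analytical Plan in section 10.0 promises descriptive statistics for tolerability and goes no further.

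**The concern.** The hypothesis can be answered only by Veterans rating the exposure treatment. The one instrument said to cover tolerability is described as rating something else: webcam-based physiology taken from recorded interviews at the assessment visits. These are different experiences. A Veteran may find daily revisiting of the trauma hard to bear and not mind the camera, or the reverse.

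If the TTSQ were used as the tolerability result, both of these Veterans would be misread. If it is not used, no Veteran-rated tolerability result for the treatment is described at all. Either way, one named component of a main aim lacks a matching measure. The ratings could not be reliably recovered once the study has closed.

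**Working it through.** There is no calculation behind this point. The only sample-size figure, 25 enrolled to give 20 completers with a 20% allowance, reproduces as 20 / (1 - 0.20) = 25, and nothing below depends on it. The check is to set what the hypothesis requires beside each measure that might supply it.

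**Required:** a rating by Veterans, of the treatment, on tolerability.

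| Measure (section) | Described content | About the treatment? | Described as tolerability? |
|---|---|---|---|
| TTSQ (9.0, Primary) | Views on adding remote physiology to assessments and on its routine use | No, as described | Yes |
| STTS-R (9.0, Primary) | Satisfaction with services and providers | Yes | No |
| Dropout/completion (9.0, Primary) | Sessions and visits attended, from the chart | Yes, in part | No, and not a rating |
| Non-compliance (9.0, Primary) | Assignments completed | Yes | No |
| CAPS-5, PCL-5, PHQ-9 (9.0, Primary) | PTSD and depression symptoms | Indirectly | No |
| SUDS (9.0, Treatment Process) | Distress level, as a gauge of arousal and engagement | Yes | No |
| PETQ (9.0, Treatment Process) | Therapist's rating of engagement and processing | Yes | No, and not Veteran-rated |
| Adverse events (11.0) | Reports at study visits | Partly | No |

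Step 1. Of the seven primary outcomes (dropout, non-compliance, STTS-R, TTSQ, CAPS-5, PCL-5, PHQ-9), one names tolerability, and its described object is not the treatment.

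Step 2. SUDS cannot simply stand in. Section 2.0 holds that emotional and physiological engagement is needed for exposure to work, so a high score is not in itself poor tolerability.

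Step 3. Attendance cannot stand in for an opinion. The dropout measure counts visits, and no reason for stopping is described as recorded. Section 8.0 does foresee the case: on a report of "intolerance for study procedures at any point during the protocol, they may be withdrawn from the study". No outcome counts such withdrawals, and that wording is not specific to exposure.

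Step 4. The Figure 1 caption does not settle the matter. Its sentence on tolerability follows the text on video-based measures and uses the same terms as the TTSQ description. It does not name the exposure sessions.

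Step 5. The TTSQ's timing conflicts. Its description in section 9.0 places it at post-treatment; the assessment schedule table marks it only at the 1-month follow-up. A Veteran would have had two recorded trauma interviews by the first point (pre- and post-treatment) and three by the second. Both points come after treatment, so Veterans who stop early may not complete the form.

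**The case against.** The strongest reply is that the plan never assigns the TTSQ to tolerability of the treatment. A reader might infer that Aim 2 will declare daily exposure tolerable on the strength of webcam ratings. The documents do not support that: section 9.0 lists the TTSQ as a primary outcome without tying it to an aim, and section 10.0 gives no variable, score or threshold. This part of the objection stands, so the consequence can only be put conditionally.

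Second, there is evidence directed at the treatment. Dropout and assignment compliance are the first two primary outcomes, Aim 2 carries a retention criterion above 80%, and section 2.0 itself moves from dropout rates to the need for better tolerability. SUDS and adverse events add to this, and the STTS-R speaks to acceptability. This narrows the gap to Veteran-rated tolerability. It does not close it, because the plan gives none of these measures that role, and attendance does not show what Veterans consider the treatment to be.

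Third, the TTSQ items are not in the documents, and the form's title includes the word Treatment. A reader might infer that none of its 14 items touches the exposure sessions; that cannot be known from a short description. If such items exist, the description in section 9.0 is incomplete and should be corrected.

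**Conclusion.** The concern holds for one component of Aim 2. As described, the protocol collects no Veteran rating of how tolerable the exposure sessions were, and the only measure that names tolerability is about the remote physiology procedures. Acceptability is partly covered by the STTS-R. Indirect evidence on tolerability exists but is not designated as such.

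No numerical size can be put on this. It is a gap in measurement, and how far ratings of the physiology procedures would differ from ratings of exposure is unknown. The conclusion rests on the protocol's description of the TTSQ being complete, and on reading the unspecified procedures in the Figure 1 caption as not clearly including treatment.

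In a single-arm pilot of 25 with descriptive reporting and no decision rule on tolerability, this is a low-cost improvement that should be made. The retention result does not depend on the TTSQ, and safety is monitored by other means.

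**What to change.** 1. Add a few Veteran items to the TTSQ on tolerability of the daily schedule, the imaginal exposure, the between-session listening and the video delivery. If such items are already on the form, correct its description in section 9.0 instead.
2. State in section 10.0 that the Aim 2 evidence is these items for tolerability, the STTS-R for acceptability, and session completion alongside.
3. Report the physiology items separately, and do not count them toward Aim 2.
4. Record the reason when a Veteran stops or is withdrawn, and report the number leaving for intolerance of treatment separately from other reasons.
5. Reconcile the TTSQ's timing between its description and the assessment schedule table.

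The cost is slightly more Veteran time, one added field on the discontinuation record and a form amendment through the IRB. Because the investigators wrote the TTSQ themselves, adding items does not alter an established scale.

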**Impact and innovation.** The goal of this proposal is in line with the priorities of the VHA and HSR&D priorities as well as the priorities of the Charleston HEROIC RIVR Pilot Project Program. Specifically, this proposal aligns with the mission stipulated in the HEROIC RFA to focus on “novel applications of telemental healthcare delivery including feasibility and/or preliminary efficacy/effectiveness trials”.

We propose that there is strong potential for broader implementation of intensive or massed exposure-based, trauma-focused treatments, and that such implementation could be even greater if virtual deployment is feasible and acceptable to patient and provider alike. Furthermore, an alternative VVC-delivered trauma- focused treatment with shorter demands on total duration

could broaden VA providers' arsenal of evidence- based interventions. This would enable greater tailoring of treatment plans to individual veteran preferences for frequency and duration of sessions as well as more flexible accommodation to daily life demands and related scheduling barriers. Taken together, we propose that establishing the safety, feasibility, and acceptability of massed exposure-based therapy delivered via VA Video Connect is a productive first step toward advancing telemental health treatment options and furthering personalized care for our veterans.

Importantly, in regards to the likelihood of impact from an implementation standpoint, all proposed VVC and therapeutic methods (imaginal exposure) in this proposal are already widely adopted across the VA system. This includes an extensive IT infrastructure for supporting VVC and the nation's largest cadre of evidence- based, trauma-focused therapists. As such, if findings from this pilot and follow up RCTs indicate safety, acceptability and efficacy, VVC-delivered massed trauma-focused therapy could be readily implemented in the VA system.

Our proposal includes unique and important contributions to veteran mental healthcare through the following innovations:

- For the first time, we will establish the safety, feasibility, tolerability, and acceptability of VVC-delivered, massed imaginal exposure for PTSD. While these aspects have been established for in-person imaginal exposure, the remote nature of VVC presents unique challenges.

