- For the first time, we will establish the preliminary efficacy of VVC-delivered, massed imaginal exposure for PTSD. While these findings will be preliminary as the study is not powered for efficacy, it will provide preliminary estimates of pre- to post- effect sizes and variance in outcomes that will aid in planning well-crafted and properly statistically powered follow up RCTs.
- COVID-19 has fundamentally altered the delivery landscape for clinical and research practice. The methods proposed here further advance the VA's capacity to promote evidence-based care and research amidst unforeseen disruptions to in-person procedures.
- For the first time, we will establish acceptability among stakeholder providers, of VVC-delivered, massed imaginal exposure for PTSD. While in-person, massed imaginal exposure has been effective in RCTs, the perceptions of evidence-based clinical providers at the forefront of treating veterans have not been assessed. In order to assess implementation likelihood, as well as to assess the need to disseminate findings and techniques, input from provider stakeholders is essential.

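### No measure described in the protocol covers providers' willingness to be trained in, or to refer to, the treatment (Exploratory Aim 1, hypothesis 2)

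*Combined protocol and SAP*

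**What the plan says.** Section 1.0 states two hypotheses under Exploratory Aim 1. The first is that "telemental healthcare providers will consider the treatment acceptable and tolerable". The second is that these providers "will be willing to receive training and/or refer patients to such services".

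Section 2.0 (Impact and innovation) gives the reason. On massed treatment it says that "such implementation could be even greater if virtual deployment is feasible and acceptable to patient and provider alike". It adds that "the perceptions of evidence-based clinical providers at the forefront of treating veterans have not been assessed" and concludes that "input from provider stakeholders is essential".

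The instrument that collects provider opinion is the TTSQ, a 14-item form written by the investigators and listed in section 9.0 under Primary Outcome Measures. Its content is given as satisfaction, acceptance, tolerability, perceived utility and "treatment outcome-related expectancies related to incorporating the remote affective physiology procedures into the assessment procedures", and also "opinions about incorporating such measures into routine care". On who answers, the text says that patients complete it too and that "providers will complete slightly different versions of this measure, addressing the same items, but adapted appropriately for wording".

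The Analytical Plan (section 10.0) provides descriptive statistics for acceptability and tolerability. It does not mention provider willingness.

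**The concern.** Hypothesis 2 is about an intention that only a clinician can report: to be trained in a therapy, or to send patients to it. The one form that asks providers for opinions is described by reference to webcam-based physiological measurement. It is also described as having the same items for patients and providers, and patients have no counterpart to a training or referral question.

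If the form is as described, the study will end with no data on hypothesis 2, and no analysis could recover them. There is a further risk for hypothesis 1: provider acceptance of the video measurement could be reported as acceptance of the therapy. Both bear on the implementation question for which section 2.0 says provider input is needed.

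**Working it through.** The plan gives no figure to reproduce here. The check is to match each described measure to the two hypotheses.

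**Count of measures.** The assessment schedule in section 9.0 has 18 rows. Primary Outcome Measures adds two outcomes taken mainly from chart review: dropout/completion and non-compliance. 18 + 2 = 20.

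**Measures completed by a clinician or provider.** Six of the 18:
- CAPS-5, MINI, C-SSRS and CGI (4) record the patient's diagnosis, symptoms, suicidality or global status.
- The PETQ (1; 8 items, completed by study therapists) rates session process, such as engagement with the trauma memory and change in beliefs.
- The provider TTSQ (1; 14 items) is the only one that asks for the provider's own opinion of anything in the study.

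4 + 1 + 1 = 6. The provider ratings mentioned at the end of the Figure 1 caption are again of engagement and processing in sessions. The STTS-R, the therapy satisfaction scale, is a patient form. The informative count is therefore one candidate instrument; most of the 20 could never have recorded provider willingness.

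**Hypothesis 2 against the TTSQ.** The nearest content is "opinions about incorporating such measures into routine care". The measures meant are most naturally the physiology measures named just before. Taking a measurement into routine care is not the same as being trained in a therapy or referring to it. Described measures covering willingness to train or refer: 0 of 20.

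**Hypothesis 1 against the TTSQ.** The count depends on how one sentence is read:
- If the words in "treatment outcome-related expectancies related to incorporating the remote affective physiology procedures into the assessment procedures" that point to the physiology procedures govern the whole list, no described measure covers provider acceptability of the therapy (0).
- If they govern only the last item of the list, or if the procedures in the Figure 1 caption include the therapy, one measure does (1, the TTSQ).

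The first reading is the more natural. The same sentence goes on to refer to such measures, and in the caption the mention of procedures follows a sentence on video-based assessment. The second is still open. The form's title includes the word Treatment, the caption as a whole covers treatment sessions as well as assessments, and section 9.0 uses the heading Treatment Procedures for the therapy.

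**Respondents.** Sections 1.0 and 2.0 speak of telemental healthcare providers and front-line clinicians. Elsewhere, in section 9.0 (Treatment Procedures) and section 13.0, a treatment provider is someone who delivers the study treatment under weekly supervision. The PETQ text names study therapists as respondents; the TTSQ text says only providers. The N = 25 in section 5.0 and the recruitment route in section 7.0 concern patients only. No provider group or number is given.

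**The case against.** The strongest reply is that the TTSQ items are not in the text available. A brief description of a 14-item form need not list every item, and the provider version is allowed to differ slightly. The appendix is not in the text either, although it is cited for the trauma interview and nothing says that it holds TTSQ items. This stands as a limit: the point concerns what is described, not what the form may contain. It does not remove the point. A form with "providers will complete slightly different versions of this measure, addressing the same items, but adapted appropriately for wording" is unlikely to carry provider-only questions, and if it does, the description is incomplete.

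A reader might infer that provider acceptability of the treatment goes unmeasured. The documents do not support that. The form's title, the alternative grammar of the sentence and the Figure 1 caption all leave room for treatment content.

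A reader might also infer that Aim 2 is undermined, because the same sentence describes the patient TTSQ. The ambiguity does carry over to patients, so it would be too much to say that Aim 2 is untouched. But Aim 2 keeps the STTS-R and the completion and compliance measures.

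It is also fair to object that training items mean little if only study therapists answer, since they already deliver the treatment. That stands, and it is why the respondents need to be named. Finally, this is one exploratory aim of a 25-person pilot with descriptive reporting, which limits the weight of the point.

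**Conclusion.** The concern holds for hypothesis 2. No described measure (0 of 20) covers providers' willingness to be trained or to refer, and the single provider-opinion form is described in terms that point elsewhere. As described, the plan cannot answer that hypothesis. Confidence is high, on the assumption that the TTSQ contains what its description says.

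For hypothesis 1 the finding is an ambiguity: zero or one instrument, depending on the reading of one sentence. Confidence in the narrower reading is moderate, and the right response is a request for clarification.

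The provider respondents are undefined, so the reach of any provider result cannot be stated at present.

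The consequence is confined largely to an exploratory aim summarised descriptively. Sample size and safety conclusions do not depend on it. It is worth fixing because the plan states the question, calls the input essential, and would otherwise not collect the answer.

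**What to change.** 1. Add to the provider TTSQ a few items on willingness to be trained in massed VVC-delivered imaginal exposure and willingness to refer patients to it. Add items on acceptability and tolerability of that treatment if they are not already there. If such items exist, correct the TTSQ description in section 9.0 instead.
2. Report answers about the therapy separately from answers about the physiology measurement, and include willingness in the descriptive summaries of section 10.0.
3. State which providers complete the form. If they are only study therapists, limit the Exploratory Aim 1 conclusion to them and do not present it as the view of telemental healthcare providers generally.

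The cost is a slightly longer provider form, an amendment to its description and possibly a narrower conclusion. Patients are asked nothing more and the sample size does not change. Reaching providers outside the study team would need a respondent group that the documents do not describe; that is a larger step and not part of this fix.
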